8 STUDY ASSESSMENTS AND PROCEDURES

8.1 SCHEDULE OF ACTIVITIES (SOA)

Procedures	Screening ¹	Enrollment ¹	Post-EGD	7 Day Follow-Up (+/-3 days)
Informed consent	X			
Eligibility Assessment	X	X		
Demographics	X			
Medical history	X			
Urine Pregnancy Test		X ²		
Routine Care EGD		X ³		
Esophageal Images		X		
Research biopsies		X ⁶		
Administer Probe ⁵		X		
Collection of Pathology Results			X ⁴	
Adverse event review and evaluation	X	X		X
Complete Case Report Forms (CRFs)	X	X	X	X

¹Screening and enrollment can occur on the same day

²Urine pregnancy tests will be performed on females with reproductive potential.

³EGD is performed as part of routine care. Subjects would be receiving this EGD regardless of participation in the study.

⁴Only if biopsies are taken for routine clinical care during the procedure. If biopsies are taken for routine clinical care during this procedure, then pathology results will be collected as part of this study, and slides may be requested from clinical biopsies for use in this study after they have yielded their results for routine care.

⁵ Probe utilized can be either the OCT probe (Cohort A) or the combined a/LCI-OCT probe (Cohort B), based on Investigator discretion at time of enrollment.

⁶ Research biopsies may be taken for participants in Cohort B.

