8.1.2 ENROLLMENT

The following procedures will be performed during the enrollment visit:

- 1) Re-assess eligibility

- 2) Completion of urine pregnancy test on women with reproductive potential
- 3) Administration of OCT-probe for Cohort A or combined a/LCI-OCT probe for Cohort B and completion of esophageal images during routine care upper endoscopy
- 4) Collection of data from endoscopy
- 5) Collection of co-localized research biopsies (Cohort B)
- 6) Adverse event assessment
- 7) Complete CRFs and data entry

For this study, an enrolled subject is defined as a subject who was successfully administered the OCT device and for whom we have evaluable data.

***Screening and enrollment can occur on the same day.

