8.1.2.3 RESEARCH BIOPSY COLLECTION AND ANALYSIS

For participants enrolled in cohort B, research biopsies will be obtained from the location of device imaging. Research biopsies are taken only if the additional biopsies do not significantly increase the patient's risk or interfere with routine care procedures. The research biopsy protocol may be modified by the physician performing the procedure if necessary. During the procedure up to 10 research biopsies may be taken for use in this study. The total number of research biopsies may vary based on presence/absence of nodularity but will not exceed 10 research-specific biopsies. This number of esophageal biopsies is within the standard of care for biopsying the esophagus. Biopsies will be immediately placed in formalin for processing and histopathological analysis by [name].

Variations to the biopsy protocol (location and number of specimens obtained) are allowable and are not considered protocol deviations.

8.1.3 7 DAY FOLLOW-UP

Enrolled subjects will be contacted 7 days (+/-3 days) after administration of the device via phone or other IRB approved method. Subjects who do not meet the definition of enrolled will not be contacted. During the 7 day follow-up, the following procedures will be performed:

- 1) Assess for adverse events
- 2) Complete eCRF and data entry

No additional follow-up is anticipated.

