9.2 SAMPLE SIZE DETERMINATION

Cohort A will be imaged with OCT. Previous data on OCT demonstrate that established systems are sensitive with respect to detecting Barrett's mucosa. For instance, Poneros et al (2001) found a 97% sensitivity rate using OCT in 38 patients²⁹. At this stage of development, if we can achieve at least 70% sensitivity, then the device will pass initial testing. If optimal sensitivity is 95%, and the lowest acceptable sensitivity is 70%, then we will require at least 14 patients with evaluable data in each group (42 total in Cohort A) to assess whether the device adequately meets this threshold with 85% power.

Cohort B will be imaged with a/LCI. Our group previously conducted and published a study in 2011 using single-point a/LCI to measure nuclear diameter as an indicator of dysplasia in the esophagus.¹³ The primary differentiating characteristic between dysplastic and normal tissue was nuclear diameter (measured by a/LCI). For dysplastic tissue, the mean nuclear diameter and standard deviation was $13.0 \pm 1.1 \mu\text{m}$, and for normal tissue, the same respective values were $10.3 \pm 1.7 \mu\text{m}$. This difference was highly statistically significant, and we rejected the null hypothesis (no difference between normal and dysplastic nuclear diameters) with a p-value of 0.0001.

To determine the number of targeted patient enrollments in Cohort B, we conducted a statistical power analysis based on our previous results. For a sample size of 20 patients with dysplasia and 20 patients with normal esophageal tissue, and targeting the same p-value of 0.0001, we expect a robust statistical power of 97% when conducting a two-sample t-test for nuclear diameter distributions matching our observations from the 2011 study. We would therefore expect a 97% chance of validating our previous observations at the same level of significance for a sample size of 20. Comparatively, for a sample size

of 10 patients in each category, our power would be only 36%, far too low; for a sample size of 30 patients in each category, our power would be greater than 99.9%, which is unnecessarily high. Therefore, for Cohort B, we will target 20 patients with dysplasia and 20 normal patients to achieve a strong statistical power without an undue excess in patient enrollment.

To accommodate Cohort B, which will be receiving the dual modality a/LCI-OCT probe, we have therefore changed the sample size to be a total of 82 (42 in Cohort A, and 40 in Cohort B).

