
9.3 POPULATIONS FOR ANALYSES

All subjects who were administered the probe, regardless of enrolling cohort, will have data included for optimization unless withdrawn per section 7.2. For this study, an enrolled subject is defined as a subject who was successfully administered the device and for whom we have evaluable data.

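### The only scheduled adverse-event contact after the procedure day is limited to subjects with evaluable data, so a probe-exposed subject without evaluable data has none

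*Combined protocol and SAP*

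**What the plan says.** Section 8.1.3 provides a single contact, by phone or another approved route, seven days after device administration with three days' leeway on either side. Its purpose is to assess adverse events (AEs) and complete the form. It goes to enrolled subjects, and the restriction is explicit: "Subjects who do not meet the definition of enrolled will not be contacted". The section adds: "No additional follow-up is anticipated".

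*Enrolled* has a special meaning here. Section 8.1.2 says: "For this study, an enrolled subject is defined as a subject who was successfully administered the OCT device and for whom we have evaluable data". Section 9.3 repeats the two conditions without naming a particular probe: "For this study, an enrolled subject is defined as a subject who was successfully administered the device and for whom we have evaluable data". For device data, Section 9.3 uses a wider set: "All subjects who were administered the probe, regardless of enrolling cohort, will have data included for optimization unless withdrawn per section 7.2".

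In the schedule of activities (Sections 1.3 and 8.1), the row "Adverse event review and evaluation" is marked at Screening, Enrollment and the 7 Day Follow-Up. The Post-EGD cell is empty. Section 8.1.2 lists "Adverse event assessment" among the enrollment-visit procedures, so a subject who reaches probe placement is assessed on that day.

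Section 8.2.5 states the AE collection window twice. One statement runs from informed consent to the end of study participation. The other covers all subjects but starts at subject enrollment. The section also has the investigator ask about AEs at each study visit, and has known events followed to resolution or stabilization.

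**The concern.** Whether a subject is asked about delayed events depends on whether the device produced usable data, not on whether the subject was exposed to it. The study tests a newly developed device in people. Section 2.3.1 lists events of endoscopy to which a device contribution may not be excludable, among them esophageal pain, bleeding and perforation, and it names a theoretical infection risk that disinfection is meant to control. Some of these could appear after the procedure day.

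Frequency also matters to the protocol's own safety rules. Section 2.3.1 treats the listed events as expected unless their nature, severity or frequency points to the device. The definitions of an unanticipated problem (8.3.1) and an unanticipated adverse device effect (8.2.3) also refer to frequency or degree of incidence. Those judgments are weaker if later events are sought in only some of the exposed subjects. Under Section 8.1.3 the study would know least about delayed events in the subjects in whom the device did not work.

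**Working it through.** No power or error-rate figure is involved, so the main check is to trace one subject through the text. Take a subject in whom the probe was attempted or placed but who has no evaluable data.

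| Place | What it provides | Does it give this subject an AE inquiry after the procedure day? |
|---|---|---|
| 8.1.2 | AE assessment at the enrollment visit | No, procedure day only |
| 8.1.2 and 9.3 with 8.1.3 | Day-7 contact for enrolled subjects | No, expressly excluded |
| 1.3 and 8.1 | AE review at Screening, Enrollment and day 7; none Post-EGD | No |
| 8.2.5, inquiry at each visit | Active question, tied to visits | No visit remains |
| 8.2.5, window from consent | Duty to record until participation ends | Duty exists, but no contact serves it |
| 8.2.5, window from subject enrollment | Collection for all subjects | No contact; may not reach this subject under the special definition |
| 8.2.5, follow-up to resolution | Covers events already known | No |
| 5.4 | Any serious event recorded for a screen failure | No contact set to find one |
| 7.3 | Missed visits and ad hoc contact | Schedules none |
| 10.1.2 and 10.1.6 | Review of unanticipated or reported events | No contact with subjects |

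The result is a recording duty with no scheduled contact behind it. The end of that duty is also unclear for this subject. The synopsis gives participation as 7 days, while Section 4.3 ties completion to the last visit or scheduled procedure, which here may be the procedure day itself.

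On timing, the call window is 7 − 3 = day 4 to 7 + 3 = day 10. The protocol neither defines evaluable nor says who judges it or when. The judgment must nevertheless be made before the call, so as late as day 10.

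**Scale of the remedy.** The stated target reproduces: 3 × 14 + 2 × 20 = 42 + 40 = 82. Section 9.2 counts Cohort A in evaluable subjects ("we will require at least 14 patients with evaluable data in each group"). For Cohort B the same follows only through the definition of enrolled. Let f be the share of exposed subjects without evaluable data. The documents give no value, so f is assumed. The smallest number exposed whose expected evaluable count reaches 82 is ceil(82 / (1 − f)):

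- f = 5%: 82 / 0.95 = 86.3, so 87 exposed and 87 − 82 = 5 not contacted
- f = 10%: 82 / 0.90 = 91.1, so 92 exposed and 10 not contacted
- f = 20%: 82 / 0.80 = 102.5, so 103 exposed and 21 not contacted

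These figures count exposed, non-evaluable subjects only. Failed placement attempts not included in f would add to them.

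**The case against.** The strongest reply is that Section 8.2.5 already covers these subjects. The duty to record AEs from informed consent does not depend on evaluability, and *subject enrollment* in the second statement may simply mean the procedure-day visit of that name. This stands as far as the duty goes. A reader might infer that the protocol drops these subjects from AE recording altogether, and the text does not support that. But a duty to record is not a means of finding out, and Section 8.1.3 expressly removes the only later contact.

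The affected group may also be small. Section 8.1.2.1 has the probe repositioned when contact is poor, some data are displayed in real time, and adequacy of contact is itself an objective, so a poor image might count as evaluable. This is fair, and it is why no size is claimed.

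The setting is low risk too: a one-time procedure, no known complications of the imaging techniques according to Section 2.3.1, procedure-day assessment, daily oversight by the clinical investigator and an independent safety monitor. That limits the severity. It does not explain why the call should go only to those whose imaging worked.

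Three stronger readings are tempting and should be resisted:

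- **Biopsied subjects are left without follow-up.** This is plausible in practice, since Cohort B biopsies follow imaging. The text does not establish it, because Sections 8.1.2.1 and 8.1.2.3 give research biopsies to subjects enrolled in Cohort B, and a strict reading of that word excludes the non-evaluable.
- **Evaluability must be settled before the window opens on day 4.** It need only be settled before the call is made.
- **Section 7.2, under which data of withdrawn subjects are not used, is part of the same gap.** It concerns a different group and is a separate matter.

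**Conclusion.** The point holds on the literal text and should be fixed. A subject in whom the probe was attempted or placed without evaluable data has no scheduled AE inquiry after the procedure day. Later events reach the study only if the subject presents for care, a monitor finds the event, or it comes to the staff's attention in some other way. This is a stated rule that weakens safety ascertainment, not an omitted detail.

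The number of subjects affected cannot be computed from the documents. The 5 to 21 above rest on an assumed 5% to 20% non-evaluable share and on requiring all 82 to be evaluable, whereas the synopsis describes 82 as an approximate upper figure. A reader might infer a biased safety estimate. The documents do not support that: the synopsis lists no endpoints and Section 9.4 plans no AE rate. The issue is completeness of ascertainment. The consent pages are not available, so any instruction to subjects to report later problems cannot be judged.

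**What to change.** - **Section 8.1.3:** give the existing day-7 AE contact to every subject in whom probe placement was attempted, unless the subject declines further contact. The call then no longer waits on a judgment of evaluability.
- **Section 8.2.5:** reconcile the two collection windows (consent and subject enrollment) with that rule, and say when participation ends for a subject who does not meet the definition of enrolled.
- **Reporting:** present AEs with probe-exposed subjects as the denominator, and state how many of them were reached at day 7. Section 9.3 already uses a probe-exposed set for optimization data.

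The cost is a wording amendment and a few more phone calls, for example 5 to 21 over the study under the assumed range. No new visit or procedure and no change to the sample size is needed.

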2.3 RISK/BENEFIT ASSESSMENT

2.3.1 KNOWN POTENTIAL RISKS

There are no known complications due to application of either a/LCI or OCT imaging techniques. Similar approaches have been previously approved by the UNC and Duke IRBs as non-significant risk device studies, and there were no safety issues in that study (UNC IRB# 07-1860).

Although the technique is not invasive, the probe itself will come in contact with esophageal tissue. For the dual modality probe (a/LCI-OCT) a small invagination in the surface of the instrument will mark the mucosa of the esophagus applied at the same location images are taken. This will aid in co-localization of research biopsies, to allow comparison of optical and histological diagnoses. We have used similar methodology in a previous study²⁶, with no adverse events noted. However, there is a theoretical risk of infection. To guard against this, the probe will be cleaned per current clinically approved methods for disinfecting endoscopy equipment which will utilize Cidex and/or Revital-Ox. Disinfection methods for this study have been reviewed and approved by the UNC Hospitals outpatient care and instrument reprocessing group. Refer to study standard operating procedures for additional information.

To date, there have been no adverse effects reported from exposure to the spectrum of light used in this device. Additionally, the device does not generate thermal injury, and because it is placed on the epithelial surface, and does not penetrate the tissue, no epithelial trauma is experienced. There is no risk of radiation from this device because the device uses only light waves.

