5.4 SCREEN FAILURES

Screen failures are defined as participants who consent to participate in the clinical trial but are not subsequently entered in the study. A minimal set of screen failure information is required to ensure transparent reporting of screen failure participants, to meet the Consolidated Standards of Reporting Trials (CONSORT) publishing requirements, and to respond to queries from regulatory authorities. Minimal information includes demography, screen failure details, eligibility criteria, and any serious adverse event (SAE).

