8.2.5 TIME PERIOD AND FREQUENCY FOR EVENT ASSESSMENT AND FOLLOW-UP

The occurrence of an adverse event (AE) or serious adverse event (SAE) may come to the attention of study personnel during study visits and interviews of a study participant presenting for medical care, or upon review by a study monitor.

All AEs will be captured on the appropriate case report form (CRF). Information to be collected includes event description, time of onset, clinician's assessment of severity, relationship to study device (assessed only by those with the training and authority to make a diagnosis), and time of resolution/stabilization of the event. All AEs occurring while on study must be documented appropriately regardless of relationship. All AEs will be followed to adequate resolution.

Any medical condition that is present at the time that the participant is screened will be considered as baseline and not reported as an AE. However, if the study participant's condition deteriorates at any time during the study, it will be recorded as an AE.

Changes in the severity of an AE will be documented to allow an assessment of the duration of the event at each level of severity to be performed. AEs characterized as intermittent require documentation of onset and duration of each episode.

Research staff will record all adverse events with start dates occurring any time after informed consent is obtained until completion of study participation. At each study visit, the investigator will inquire about the occurrence of AE/SAEs since the last visit. Events will be followed for outcome information until resolution or stabilization.

All new or worsening adverse events (AEs) will be collected for all subjects from the time of subject enrollment through completion or termination of the clinical investigation. This includes AEs that are not device or procedure related.

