10.1.6 SAFETY OVERSIGHT

Monitoring for the trial will occur at several levels. On a daily basis, the clinical study PI will monitor any adverse events in subjects enrolled in the trial. In addition to performing the endoscopies, and, in conjunction with other study personnel, the clinical study PI will supervise other study-related activities and be well-positioned to evaluate the safety of the intervention. Additionally, the study will comply with all monitoring regulations of UNC and Duke's IRBs. The study will also have a formal Independent Safety Monitor (ISM), [name], MPH. [name] is a faculty member at UNC who has extensive experience in the care of subjects with Barrett's esophagus, and no connection to the trial. [name] will perform review of any reported adverse event within a week of occurrence or within a week of the study team's knowledge of the event, whichever is applicable. As events occur, the monitor will characterize each event in terms of relatedness, expectedness, severity, and seriousness. These AEs will be reported to the IRB and the NIH according to their specified reporting time frames.

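### The day-7 adverse-event contact, the only one scheduled after the procedure, leaves out subjects in whom the probe was used but failed or gave no evaluable data

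*Combined protocol and SAP*

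**What the plan says.** Section 8.1.3 has enrolled subjects contacted 7 days (±3) after device administration to ask about adverse events, and states: "Subjects who do not meet the definition of enrolled will not be contacted". It expects no further follow-up.

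Section 8.1.2 gives the definition: "an enrolled subject is defined as a subject who was successfully administered the OCT device and for whom we have evaluable data". Section 9.3 repeats both conditions.

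The schedules of activities in 1.3 and 8.1 place AE review at screening, at the enrollment (endoscopy) visit and at day 7. The post-EGD column has none.

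Other AE provisions:

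- Section 8.2.5: "Research staff will record all adverse events with start dates occurring any time after informed consent is obtained until completion of study participation". A later paragraph of the same section says that new or worsening events "will be collected for all subjects from the time of subject enrollment through completion or termination of the clinical investigation".
- Section 5.4 asks for any serious adverse event (SAE) in screen failures.
- Section 10.1.6: "the clinical study PI will monitor any adverse events in subjects enrolled in the trial". The independent safety monitor "will perform review of any reported adverse event within a week of occurrence", or within a week of the team learning of it.

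**The concern.** The definition of enrolled serves to count subjects towards the sample size. Section 8.1.3 reuses it to decide who is followed for harm, so follow-up depends on the device having worked. Exposure does not: the probe touches the esophagus whether or not the images are usable.

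Failures are foreseeable. The first objective (section 3) is whether adequate tissue contact can be attained at all, and 8.1.2.1 describes poor-contact images and tells the operator to reposition the probe.

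Of contact between the probe and the tissue, section 2.3.1 says: "However, there is a theoretical risk of infection". An infection would not normally show itself on the day of the endoscopy, and it has no evident link to image quality. What is at stake is that a delayed event in an exposed subject goes unnoticed unless that subject comes forward.

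**Working it through.** This is mainly a check of the text. The plan states no figure for this point, so there is none to reproduce.

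**Step 1: who is exposed but not enrolled.** Enrolled requires successful administration and evaluable data. Failing either condition removes the subject from the day-7 contact, even though the probe was introduced.

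**Step 2: what remains for that subject.**

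| Provision | Reaches an exposed, non-enrolled subject? | Seeks events after the procedure day? |
|---|---|---|
| 8.1.2, AE assessment at the endoscopy visit | Yes | No |
| 8.1.3, day-7 contact | No, by explicit rule | Yes |
| 8.2.5, recording from consent to end of participation | Yes | No contact is attached to it |
| 8.2.5, collection from subject enrollment | Unclear, given the definition | No contact is attached to it |
| 5.4, SAEs in screen failures | If classed as a screen failure | No contact is attached to it |
| 10.1.6, daily monitoring by the PI | Not on the strict definition | Not stated |
| 10.1.6, independent monitor | Only if an event is reported | No |

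The day-7 contact is the only scheduled step that looks for delayed events, and it is the one these subjects do not get.

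**Step 3: can research biopsies be involved?** Sections 8.1.2.1 and 8.1.2.3 provide biopsies for those enrolled in Cohort B, after imaging and at the imaged site. Section 6.1 says that only some optical data are shown in real time, while all are stored for post hoc analysis. If evaluability is judged from the stored data, a subject could have biopsies and later prove non-evaluable. The protocol does not say when evaluability is judged, so this is possible but not established.

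**Step 4: how many subjects.** Inputs: N = 82 (section 9.2: 3 × 14 + 2 × 20 = 42 + 40). The non-evaluable fraction f among exposed subjects is not in the documents, so 5%, 10% and 20% are assumed. It is also assumed that 82 evaluable subjects are reached. Section 9.2 counts Cohort A explicitly in evaluable patients, but the synopsis gives 82 as an approximate upper figure.

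Exposed but not contacted = N × f / (1 − f):

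- f = 5%: 82 × 0.05 / 0.95 = 4.3, about 4
- f = 10%: 82 × 0.10 / 0.90 = 9.1, about 9
- f = 20%: 82 × 0.20 / 0.80 = 20.5, about 21

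**Step 5: scale of risk.** Section 2.3.3 puts bleeding from endoscopic biopsies below 1/1,000 and perforation or infection lower still. Taking 1/1,000 as a per-subject risk p, purely for scale, the chance of at least one such event in n uncontacted subjects is 1 − (1 − p)^n:

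- n = 4: 1 − 0.999^4 = 0.4%
- n = 9: 1 − 0.999^9 = 0.9%
- n = 21: 1 − 0.999^21 = 2.1%

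The 1/1,000 figure concerns biopsy bleeding. It is not a rate for all delayed events, and the documents give none for the new probe.

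**The case against.** The strongest reply is that this is a low-risk pilot and the gap may seldom arise. Evaluable data is undefined. Since adequacy of contact is itself an objective, poor images might count as evaluable for that purpose. Several sites are imaged per subject and the probe can be repositioned, so one poor site need not make the subject non-evaluable. The infection risk is called theoretical and disinfection is specified. Section 2.3.1 reports no perforation and no endoscopic treatment for bleeding in more than 5,000 earlier research-biopsy patients. Same-day assessment, AE recording from consent and independent review of reported events all remain.

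Most of this stands. It keeps the likely number and the absolute risk small. It does not remove the rule in 8.1.3, and none of the remaining provisions asks the subject anything after the procedure day.

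A reader might also infer more than the documents support:

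- *That AEs in these subjects are not captured at all.* Section 8.2.5 records events from consent, and the endoscopy visit includes an AE assessment.
- *That reported AE rates will be biased.* Section 9.1 names incidence rates only as a generic example, and 9.4 plans no AE analysis. Any bias would also need a higher risk after failed use, for which the documents give no evidence.
- *That many biopsied subjects go unfollowed.* Biopsies are for those enrolled in Cohort B, so multiplying every failure by the maximum of 10 biopsies has no basis.
- *That section 7.2 discards these subjects' safety data.* That rule concerns withdrawn or terminated subjects. A non-evaluable image is not a withdrawal, and 9.3 keeps data from all who were administered the probe unless withdrawn.

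**Conclusion.** The point holds as a limited gap in safety follow-up. By an explicit sentence, the only scheduled AE contact after the procedure is withheld from subjects exposed to the probe without evaluable data. They get same-day assessment and passive reporting, but no active search for delayed harm.

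The number affected is unknown. The figures of about 4, 9 or 21 depend on assumed non-evaluable fractions and on reaching 82 evaluable subjects, and would be smaller if poor images count as evaluable. Inclusion of biopsied subjects depends on evaluability being judged after the procedure. The documents suggest a low absolute risk and give no ground for expecting a particular number of missed events.

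The case for changing the rule is that exposure, not image quality, should decide who is asked about harm, and that the change is cheap.

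**What to change.** In 8.1.3, replace the exclusion sentence with: *All subjects in whom the probe was introduced, or from whom a research biopsy was taken, will be contacted 7 days (+/-3 days) after the procedure, whether or not they meet the definition of enrolled.*

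Align two other places: in 10.1.6, make the PI's daily monitoring cover these exposed subjects and not only those enrolled; in 8.2.5, replace the enrollment starting point so that it agrees with the recording from consent stated earlier in that section.

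The definition of enrolled can stay for counting towards the sample size. Consented subjects with neither exposure need no call.

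The cost is an IRB amendment and one extra phone call, on the existing AE form, per exposed non-enrolled subject: about 4 to 21 calls over the study under the fractions assumed above.
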